**7.2.3. E-RS: COPD Total and Subscale Scores Responder Analysis**

**7.2.3.1. Endpoint**

Response according to E-RS: COPD total score, subscale scores, SGRQ total score or CAT score as defined in Section 14.6.3.

**7.2.3.2. Summary Measure**

Ratio of odds of being a responder vs. not for each danirixin dose vs. placebo

**7.2.3.3. Population of Interest**

PP population

**7.2.3.4. Strategy for Intercurrent (Post-Randomization) Events**

A ‘hypothetical’ strategy will be used to account for the intercurrent events of occurrence of a protocol deviation considered to impact efficacy during the treatment period (see Appendix 1) and treatment discontinuation, to estimate the effect if participants had not deviated from the protocol and remained on treatment. Only response data prior to the occurrence of a protocol deviation considered to impact efficacy or treatment discontinuation will be used in the analysis. Subsequent data up to Month 6 will be assumed to be missing at random (MAR).

**7.2.3.5. Statistical Analyses / Methods**

**7.2.3.5.1. Statistical Methodology Specification**

Endpoint / Variables

 
• Response according to E-RS: COPD total score, subscale scores, SGRQ total score or CAT score
 

Model Specification

 
• Generalized linear mixed model
 
• Terms in the model:             
 
○ Dependent : response (yes/no)
 
○ Categorical : treatment group, smoking status (screening), country, visit/month
 
○ Continuous : baseline
 
○ Interaction : baseline*visit/month, treatment group*visit/month
 
 
 
• The model will be fit with an unstructured variance-covariance matrix with one single model to include all visits/months where the assessment in question is scheduled to be performed.
 
• Computation of confidence intervals for the odds ratios is based on the individual Wald tests.
 

Model Checking & Diagnostics

 
• Pearson residuals will be plotted by using PLOTS=PEARSONPANEL option for the model statement in SAS.
 

Model Results Presentation

 
• Number and percentage of responders and non-responders for each treatment at each visit/month
 
• Odds ratio for comparison of each danrixin dose with placebo, with associated 90% CI and p-value
 

#### 7.2.4. SGRQ Total Score and CAT Score

SGRQ total score and CAT score at each visit will be analysed using the same methodology as for E-RS: COPD total and subscale scores longitudinal analysis (as described in Section 7.1.3.5.1). Visit will be substituted for Month. A figure of mean and 90% CIs for each treatment over time will be generated for SGRQ Total Score and CAT Score.

#### 7.2.5. Rescue Use

The monthly mean number of puffs of rescue use per day according to diary card data and the monthly mean number of occasions of rescue use per day according to sensor data and the monthly percentage of rescue-free days according to diary card data and according to sensor data will be analysed using the same methodology as for E-RS: COPD total and subscale scores longitudinal analysis (as described in Section 7.1.3.5.2). A figure of daily mean number of puffs of rescue medication per day using diary data over time and daily mean number of occasions of rescue medication per day using sensor data over time will be generated for the PP population.

Additional analysis of rescue use according to sensor data may be performed and will be defined in a separate RAP.

#### 7.2.6. Physical Activity

Assessment of physical activity during clinical visits (C-PPAC) has been developed to capture experience of physical activity in participants with COPD. This physical activity data will be combined with activity monitor data to assess physical activity experience according to the IMI PROactive User Guide (14JUN16). A PROactive Total Score and two domain scores (amount and difficulty) will be derived.

Raw and change from baseline PROactive Total Score and Domain scores (Amount and Difficulty) will be summarized.

For the strategic interim, the responses to the C-PPAC questions at each visit will be summarized.

Additional analysis of activity monitor data may be performed and will be defined in a separate RAP.

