3.1. Study Rationale

This protocol describes a Phase IIb dose-ranging study evaluating the clinical activity and safety of danirixin compared with placebo in participants with COPD that have current respiratory symptoms including cough, increased sputum production, and dyspnoea. Study participants will continue with their standard of care inhaled medications (i.e. long acting bronchodilators with or without inhaled corticosteroids) while receiving study treatment. In this study, 5 doses of danirixin and placebo are being evaluated (danirixin or placebo will be taken orally twice daily).

The primary objectives of the study are to evaluate the dose response of danirixin compared with placebo on respiratory symptoms assessed by the E-RS:COPD patient reported outcome (PRO) tool and assess the safety of danirixin compared with placebo. Key secondary objectives include an evaluation of danirixin compared with placebo on healthcare resource utilization (HRCU) defined COPD exacerbations, health status, physical activity, and rescue medication use. Exploratory objectives will include blood biomarkers to investigate the impact of danirixin on biomarkers of extracellular matrix turnover and remodeling.

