4. OBJECTIVES AND ENDPOINTS

Objectives	Endpoints

Primary
 
 • To characterize the dose response of danirixin compared with placebo on the incidence and severity of respiratory symptoms in participants with COPD • To compare the safety of danirixin with placebo in participants with COPD 	
 • Change from baseline in respiratory symptoms measured by E-RS:COPD daily diary at month 6: total score and subscales (i.e. breathlessness, cough and sputum, and chest symptoms) • Adverse events (AE), clinical laboratory values, vital signs, electrocardiogram (ECG)

Objectives	Endpoints

Secondary
 
 • To characterize the dose response of danirixin compared with placebo on the annual rate of moderate/severe COPD exacerbations in participants with COPD • To further characterize the clinical activity of danirixin compared to placebo in participants with COPD 	
 • Healthcare Resource Utilization (HCRU)-defined COPD exacerbations • E-RS:COPD Responder Analysis (including subscales) • Number of Exacerbations of Chronic Pulmonary Disease (EXACT) tool defined events • Time to first EXACT event • EXACT event severity • EXACT event duration for all events • Time to first HCRU-defined COPD exacerbation • Time to first severe HCRU-defined COPD exacerbation • HCRU-defined exacerbation duration • Change from baseline for the St. George's Respiratory Questionnaire (SGRQ) total score (derived from SGRQ-C) • SGRQ responder analysis • Change for baseline COPD Assessment Test (CAT) total score • CAT responder analysis • Lung function (FEV1, FEV1 % predicted, FVC, FEV1/FVC ratio) • Rescue medication use • Participant experience of physical activity (subset of approximately 50% of participants) measured using PROactive Clinic Visit Tool (C-PPAC)

Objectives	Endpoints

 To characterize the pharmacokinetics of danirixin in participants with COPD 	
 Danirixin concentration and standard pharmacokinetic parameters for danirixin (e.g. AUC, Cmax, Tmax), using dried blood spot data

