10.5.1.2. Key Secondary Analyses

All analyses for other efficacy endpoints will use the mITT Population, unless otherwise noted. Dose will be treated as a categorical variable and no dose response modelling will be done unless otherwise stated. The treatment comparisons of interest will be between individual danirixin doses and placebo and between different danirixin doses. Smoking status (current vs former) will be included as a covariate in all analyses. All Bayesian analyses will use non-informative priors. Further details will be described in the RAP.

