2.48	2.36	PP		Analysis of Change from Baseline in Monthly Mean Number of Puffs of Rescue Medication per Day using Diary Data up to Month 6	MMRM on Change from Baseline	StInt, SAC
2.49	2.37	PP	PD4	Summary of Baseline Percentage Rescue-free Days using Diary Data	Include total column	StInt, SAC
2.50	2.38	PP	PD4	Summary of Percentage Rescue-free Days using Diary Data up to Month 6	Include raw and change from baseline	StInt, SAC
2.51	2.39	PP		Analysis of Change from Baseline in Percentage Rescue-free Days using Diary Data up to Month 6	MMRM on Change from Baseline	StInt, SAC

Efficacy: Tables						
StInt No.	SAC No.	Population	IDSL / Example Shell	Title	Programming Notes	Deliverable [Priority]
	2.40	PP	PD4	Summary of Baseline Mean Number of Occasions of Rescue Medication per Day using Sensor Data	Include total column	SAC
	2.41	PP	PD4	Summary of Monthly Mean Number of Occasions of Rescue Medication per Day using Sensor Data up to Month 6	Include raw and change from baseline	SAC
	2.42	PP		Analysis of Change from Baseline Monthly Mean Number of Occasions of Rescue Medication per Day using Sensor Data up to Month 6	MMRM on Change from Baseline	SAC
	2.43	PP	PD4	Summary of Baseline Percentage Rescue-free Days using Sensor Data	Include total column	SAC
	2.44	PP	PD4	Summary of Percentage Rescue-free Days using Sensor Data up to Month 6	Include raw and change from baseline	SAC
	2.45	PP		Analysis of Change from Baseline Percentage Rescue-free Days using Sensor Data up to Month 6	MMRM on Change from Baseline	SAC
Physical Activity						
	2.46	PP	PD4	Summary of Baseline PROactive Score	Include total column Endpoints: PROactive Total Score and domain scores	SAC
	2.47	PP	PD4	Summary of PROactive Score up to Month 6	Include raw and change from baseline Endpoints: PROactive Total Score and domain scores	SAC

Efficacy: Tables						
StInt No.	SAC No.	Population	IDSL / Example Shell	Title	Programming Notes	Deliverable [Priority]
2.52		PP		Summary of Responses to C-PPAC Questionnaire at Each Visit		StInt
Subject Global Assessments						
	2.48	PP	PD4	Summary of Subject Global Assessments at Baseline	Include total column Endpoints: severity, activity limitation	SAC
	2.49	PP	PD4	Summary of Subject Global Assessments	Endpoints: severity, change in severity, activity limitation and change in activity limitation	SAC

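### The SAP pre-specifies no dose-versus-placebo estimate for C-PPAC physical activity, a secondary endpoint that the protocol says will be compared with placebo, and does not list this as a change

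*SAP*

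**What the plan says.** Protocol 3.1 states: "Key secondary objectives include an evaluation of danirixin compared with placebo on healthcare resource utilization (HRCU) defined COPD exacerbations, health status, physical activity". The synopsis, under Overall Design, likewise names physical activity among the outcomes on which dose response relative to placebo is evaluated. In Protocol 4, C-PPAC is a secondary endpoint in a subset of about 50%, under the objective "To further characterize the clinical activity of danirixin compared to placebo in participants with COPD".

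Protocol 10.5.1.2, which covers the efficacy endpoints other than the primary, says: "The treatment comparisons of interest will be between individual danirixin doses and placebo and between different danirixin doses". It adds: "Smoking status (current vs former) will be included as a covariate in all analyses". It leaves further detail to the analysis plan.

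For C-PPAC, SAP 7.2.6 derives the PROactive total, amount and difficulty scores and then says: "Raw and change from baseline PROactive Total Score and Domain scores (Amount and Difficulty) will be summarized". The display list in SAP 14.11.5 has a baseline summary (Table 2.46) and "Summary of PROactive Score up to Month 6" (Table 2.47). There is no analysis table, and SAP 14.11.6 has no PROactive figure. SAP 7.2.6 also allows an optional further analysis of the activity monitor data under a separate plan.

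**The concern.** A randomised comparison with placebo is announced for this endpoint, but the SAP stops at describing each arm. Under SAP 14.5.2 a continuous summary gives the number of participants, mean, SD, median, minimum and maximum. It gives no contrast, interval or covariate adjustment. SAP 7.2 defines the secondary estimand as an effect of actual treatment, yet 7.2.6, which sits under that heading, estimates no effect.

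The neighbouring endpoints are handled differently. SGRQ, CAT and rescue use all receive a repeated-measures model (SAP 7.2.4 and 7.2.5). SAP Table 1 records changes from the protocol as small as a switch in the word used for participants, but not this one.

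About 300 people (50% of 600) would wear a monitor for three periods without any planned treatment estimate. Readers would compare unadjusted arm means by eye. Any formal comparison would be chosen after the data are seen, across five doses and three scores.

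**Working it through.** **What is promised and what is planned**

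- Comparison with placebo: promised in the synopsis and Protocol 3.1, 4 and 10.5.1.2. No contrast is planned in SAP 7.2.6 or Tables 2.46 and 2.47.
- Smoking status as a covariate: stated in Protocol 10.5.1.2 for all analyses. No covariate can enter a summary table.
- Record of the change: none in SAP Table 1.
- Optional separate plan: conditional, undefined and limited to activity monitor data, so it does not cover the total or difficulty score.

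**What a modelled comparison would give**

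The documents state no SD, target difference or power for C-PPAC. The sample size statement in Protocol 10.2 concerns E-RS:COPD under an Emax fit, so there is no C-PPAC figure to reproduce. Results below are in SD units of the C-PPAC score.

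Inputs: about 600 randomised equally to six arms (Protocol 5.2, 10.3); about 50% in the activity subset (Protocol 4); about 10% dropout (Protocol 5.2); two-sided 90% intervals (Protocol 10.5). Assumption: the subset divides evenly over the arms.

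- Per arm: 600 × 0.5 / 6 = 50 at entry; 50 × 0.9 = 45 at Day 168.
- Unadjusted half-width: 1.645 × √(2/n). For n = 50 this is 0.329 SD; for n = 45 it is 0.347 SD.
- Baseline-adjusted half-width at n = 45: 0.347 × √(1 − ρ²), where ρ is the assumed correlation between baseline and Day 168.
- Crude change-from-baseline half-width at n = 45: 0.347 × √(2(1 − ρ)). A reader could obtain this from Table 2.47.

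| Assumed ρ | Adjusted (SD) | Crude change (SD) |
|---|---|---|
| 0.3 | 0.331 | 0.410 |
| 0.5 | 0.300 | 0.347 |
| 0.7 | 0.248 | 0.269 |
| 0.9 | 0.151 | 0.155 |

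- Difference detectable with 80% power, unadjusted, n = 45: (1.645 + 0.842) × √(2/45) = 0.52 SD. Power is 0.41 for a true difference of 0.3 SD and 0.77 for 0.5 SD.
- Number of contrasts: 5 doses × 3 scores × 2 visits = 30.

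Forty-five per arm is an upper figure. A valid score needs a complete questionnaire and at least three days with eight hours' wear (SAP 14.6.3), and per-protocol exclusions (SAP 14.1.1) remove more.

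**The case against.** The strongest reply is that description is a reasonable choice for a half-sample endpoint in a dose-ranging trial. The trial has no formal primary hypothesis (SAP 2.4) and no multiplicity adjustment (SAP 5.5). Other secondary endpoints, such as FEV1/FVC ratio and exacerbation duration, are also only summarised. Protocol 10.5.1.2 names comparisons of interest and defers the detail, so it is arguable whether a descriptive choice is a change that Table 1 had to record. The proposed contrasts are many and individually weak, and at high correlation the adjusted estimate is little more precise than a crude change-score difference.

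Much of this stands as a reason to read the results as estimates and not as tests. It does not explain why SGRQ, CAT and rescue use are modelled while C-PPAC is not, or why the plan gives no reason.

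Two stronger readings are tempting and are not supported:

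- A reader might infer that the trial cannot answer the physical activity objective. It can. C-PPAC is scheduled in every arm of the subset at Visits 3, 7 and 10, and an unadjusted difference and interval follow from the tabulated n, mean and SD. The formal objective is also served by several modelled endpoints.
- A reader might infer from Protocol 3.1 that C-PPAC is a key secondary endpoint. The synopsis list under that label contains only the exacerbation rate, time to first exacerbation and SGRQ total score. Protocol 4 lists C-PPAC as an ordinary secondary endpoint.

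**Conclusion.** The point holds as a gap in pre-specification. The protocol says this secondary endpoint will be compared with placebo; the SAP plans no estimate of that comparison and does not say that it has been dropped. What is missing is a planned, baseline-adjusted contrast. The data to form one are collected.

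With at most about 45 per arm, the 90% half-width is about 0.35 SD unadjusted and about 0.33 to 0.15 SD adjusted. These figures rest on even spread of the subset over arms, 10% dropout and assumed correlations of 0.3 to 0.9, none of which the documents establish for C-PPAC. The gain is mainly that the estimate is fixed in advance of the final analysis and adjusted in the same way as its neighbours; the gain in precision over a crude change score may be small.

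A minor separate point concerns FEV1 % predicted, a named secondary endpoint (Protocol 4, SAP 2.2). It has no post-baseline display in SAP 8.4 or Tables 3.28 to 3.37. The loss is slight, because post-bronchodilator FEV1 in litres is already modelled against placebo.

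**What to change.** In SAP 7.2.6, apply the frequentist MMRM of 7.1.3.5.2 to change from baseline in the PROactive total, amount and difficulty scores in the activity subset, with visit (Days 84 and 168) in place of month. Report each dose minus placebo with a 90% confidence interval at both visits, and add the tables to 14.11.5.

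State two limits in the text:

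- The Schedule of Activities has no PROactive assessment at Early Withdrawal, so the model relies on data after discontinuation being missing at random.
- The analysis is being added after the unblinded strategic interim (SAP 3.1.3), at which C-PPAC questionnaire responses were to be summarised, and should be labelled so.

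Record the addition in the amendment history. If the sponsor prefers description only, SAP Table 1 should say so and give the reason; that removes the undeclared discrepancy but still leaves no estimate.

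The cost is SAP wording and three more runs of a model already specified, with no new data collection. The downside is 30 low-power contrasts without multiplicity adjustment, to be presented as estimates. FEV1 % predicted can be put through the 8.4.5.1 model in one further run.

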### 7.3. Exploratory Efficacy Analyses

#### 7.3.1. E-RS: COPD Total Score

For the final analysis the list of subgroups may be amended.

Exploratory Statistical Analyses
Model Specification

For the PP population, an assessment of whether the effect of treatment on E-RS: COPD Total Score is modified by:
 
 
○ Baseline E-RS: COPD Total Score (continuous) (Strategic Interim only)
 
○ Smoking Status at Screening
 
○ Country (Strategic Interim only)
 
 
will be made by fitting separate repeated measures models, identical to the MMRM model described in Section 7.1.3.5.2 but also including additional terms for the treatment by factor interaction.
 
An assessment will be made of whether the effect of treatment on E-RS: COPD Total Score is modified by the following factors (as defined in Section 5.4.2):
 
 
○ Percent Predicted FEV1 at Screening (continuous)
 
○ Baseline CAT Score (continuous)
 
○ Exacerbation history (Strategic Interim only)
 
○ COPD Medication at Baseline (Strategic Interim only)
 
○ CMH status at baseline (Strategic Interim only)
 
○ Season (Strategic Interim only)
 
 
This will be made by fitting separate repeated measures models, identical to the model described above but also including additional terms for the factor and the treatment by factor interaction.
 
If an interaction from these analyses is significant at the 10% level it implies that the effect of treatment on E-RS: COPD Total Score is modified by the factor. The analysis will be run by each level of the factors as listed below regardless of significance level (excluding any groups with sparse data):
 
 
○ Baseline E-RS: COPD Total Score <10, ≥10 (Strategic Interim only)
 
○ Smoking Status at Screening - Former, Current
 
○ Country (Strategic Interim only)
 
○ Percent Predicted FEV1 at Screening <50, ≥50
 
○ Baseline CAT Score <10, ≥10
 
○ Exacerbation history (history of ≥2 moderate/severe exacerbations, <2 moderate/severe exacerbation) (Strategic Interim only)
 
○ COPD Medication at Baseline (ICS+LABA+LAMA vs. ICS+LABA vs. LABA+LAMA vs. Other COPD medication) (Strategic Interim only)
 
○ CMH +, - (Strategic Interim only)
 
○ Season (The estimates from this model will be presented for each season.) (Strategic Interim only)
 

Model Checking & Diagnostics

 
● Distributional assumptions underlying the model used for analyses using MMRM will be examined by obtaining a normal probability plot of the residuals and a plot of the residuals versus the fitted values (i.e. checking the normality assumption and constant variance assumption of the model respectively) to gain confidence that the model assumptions are reasonable. Plots of residuals versus covariates and baseline versus response will also be examined.
 

Exploratory Statistical Analyses
Model Results Presentation

 
• The interaction p-values from the interactions of treatment with the factors above will be presented.
 
• Comparisons of each danirixin dose with placebo for each level of each categorical subgroup.
 
• LS Mean changes from baseline estimates for each treatment by visit (except for season) along with 90% CIs will be obtained for each level of the subgroup.
 
• LS Mean changes from baseline estimates for each treatment along with 90% CIs will be obtained for each level of the season subgroup.
 
• LS Mean changes from baseline estimates and 90% CIs will be plotted against treatment in separate panels for each level of the factor for Month 6 (except for season).LS Mean changes from baseline estimates and 90% CIs will be plotted by treatment for each level of the season subgroup.
 
• If an interaction between treatment and factor is significant at the 10% level an additional plot of LS Mean changes from baseline and 90% CIs against treatment by Month will be produced with a separate plot for each level of the factor (except for season).
 

### **7.3.2. CAT Score**

CAT score will be analysed using the same methodology as for E-RS: COPD total scores exploratory statistical analysis (as described in Section 7.3.1).

### **7.3.3. Time to First Clinically Important Deterioration**

Following the Strategic Interim, the study team decided not to report this exploratory endpoint.

### **7.3.4. SGRQ Domain Scores**

Raw and change from baseline SGRQ domain scores will be summarized.

### **7.3.5. Participant Global Assessments**

Participant global assessments of severity, change in severity, activity limitation and change in activity limitation will be summarized.

## **8. SAFETY ANALYSES**

Details of the planned displays including the population to be used for each display and which displays are produced for the strategic interim are presented in [Appendix 11](#). Additional details are provided below.

The estimand is the effect of actual treatment in the population of participants who were randomized and dosed. All collected data will be included in reporting as described below. Non-recorded missing data following study withdrawal will not be imputed.

### **8.1. Adverse Events Analyses**

Adverse events analyses including the analysis of AEs, SAEs and other significant AEs will be based on GSK Core Data Standards.

### **8.2. Adverse Events of Special Interest Analyses**

AESI have been defined as AEs which have specified areas of interest for the COPD population. A list of Standardized Medical Dictionary for Regulatory Activities (MedDRA) Queries (SMQs) and other groupings for AESI is provided in [Section 14.6.4](#)

